7.1.1. Packaging and Labeling

Mirikizumab and placebo will be supplied to the investigator by Lilly or its designee. Clinical trial materials will be labeled according to the country's regulatory requirements. All investigational products will be stored, inventoried, reconciled, and destroyed according to applicable regulations. Clinical trial materials are manufactured in accordance with current Good Manufacturing Practices (GMP).

Study drug will be supplied as:

- Single-use solution pre-filled syringe containing mirikizumab or placebo. The 1-mL syringe of mirikizumab is manufactured to deliver 100 mg.
- Single-use solution vial containing mirikizumab. The 15-mL vial of mirikizumab is manufactured to deliver 300 mg (20 mg/ml).

Mirikizumab cannot be distinguished visually from placebo.

Study drug will be provided with study-specific labels. Syringes and vials will be supplied in cartons, with the appropriate quantity specific to the planned dispensing schedule of the investigational product. No concomitant UC therapies will be provided by Lilly or its designee.

7.2. Method of Treatment Assignment

Assignment to treatment groups for patients entering Study AMBG as clinical responders will be determined by a computer-generated random sequence using an interactive web-response system (IWRS) in a double-blind manner. To achieve between-group comparability, patients will be stratified to these arms based upon biologic-failed status (yes or no), baseline corticosteroid use (yes or no), region (North America/Europe/Other), and induction remission status (yes or no). This stratification will be controlled by IWRS.

7.2.1. Selection and Timing of Doses

The doses will be administered at each scheduled visit as described in the Schedule of Activities (Section 2). The actual time of all dose administrations will be recorded in the patient's electronic case report form (eCRF). Doses, other than rescue mirikizumab IV doses, should not be administered during unscheduled visits, unless the unscheduled visit occurs during the next scheduled dosing window. Rescue mirikizumab IV doses may be administered during unscheduled visits if LOR has been confirmed and if it is ≥ 7 days from the most recent SC dose. Subsequent rescue mirikizumab IV doses will be given every 4 weeks (+/- 3 days) for total of 3 doses.

7.3. Blinding

This is a double-blind study. To preserve the blinding of the study, a minimum number of Lilly personnel will have access to the randomization table and treatment assignments before the study

is complete. These personnel will not have communication with site personnel. No unblinding at the investigational site for investigational product preparation will be required. A blinded study site pharmacist or other trained and qualified person will prepare the investigational product.

Emergency unblinding for AEs may be performed through the IWRS, which may supplement or take the place of emergency codes generated by a computer drug-labeling system. This option may be used ONLY if the patient's well-being requires knowledge of the patient's treatment assignment. All notifications resulting in an unblinding event are recorded and reported by the IWRS.

In case of an emergency, the investigator has the sole responsibility for determining if unblinding of a patient's treatment assignment is warranted for medical management of the event. The patient's safety must always be the first consideration in making such a determination. If a patient's treatment assignment is unblinded, Lilly must be notified immediately. If the investigator decides that unblinding is warranted, it is the responsibility of the investigator to promptly document the decision and rationale and notify Lilly as soon as possible.

If an investigator, site personnel performing assessments, or patient is unblinded, the patient must be discontinued from the study drug and must complete the ETV and post-treatment follow-up as per protocol. In cases where there are ethical reasons to have the patient remain on study drug, the investigator must obtain specific approval from the sponsor or designee for the patient to continue in the study.

7.4. Dosage Modification

Dose adjustments, other than the dose regimen change provided to patients who demonstrate a LOR, described in Section 7.1, are not permitted in this study.

7.5. Preparation/Handling/Storage/Accountability

The investigator or his/her designee is responsible for the following:

- Confirming appropriate temperature conditions have been maintained during transit for all study treatment received and any discrepancies are reported and resolved before use of the study treatment.
- Ensuring that only participants enrolled in the study may receive study treatment and only authorized site staff may supply or administer study treatment. All study treatments must be stored in a secure, environmentally controlled, and monitored (manual or automated) area in accordance with the labeled storage conditions with access limited to the investigator and authorized site staff.
- The investigator, institution, or the head of the medical institution (where applicable) is responsible for study treatment accountability, reconciliation, and record maintenance (such as, receipt, reconciliation, and final disposition records).

Detailed instructions regarding supplies and preparation and handling of mirikizumab will be provided by the sponsor.

Investigational products will be supplied by Lilly or its designee, in accordance with current GMP and will be supplied with lot numbers, expiry dates, and certificates of analysis, as applicable.

Mirikizumab and placebo should be stored in refrigerated conditions 2°C to 8°C (36°F to 46°F).

7.6. Treatment Compliance

All doses of study medication will be administered at the study site by site personnel. Deviations from the prescribed dosage regimen should be recorded in the eCRF.

Every attempt will be made to select patients who have the ability to understand and comply with study instructions. The investigator is responsible for discussing methods to ensure high treatment compliance with the patient before randomization.

If a patient is noncompliant with study procedures and/or investigational product administration, the investigator should assess the patient to determine the reason for noncompliance and educate and/or manage the patient as appropriate to improve compliance. If, in consultation with Lilly or its designee, the noncompliance is deemed to be significant such that it affects the safety of the patient or the evaluation of the efficacy and safety data in this study, the patient may be discontinued from the study.

7.7. Concomitant Therapy

All concomitant medications taken during the study must be recorded in the Concomitant Medication eCRF. All patients are encouraged to maintain their usual medication regimens for concomitant conditions or diseases throughout the study, unless those medications are specifically excluded ([Appendix 8](#)).

Patients taking permitted UC concomitant medications, other than oral corticosteroids, are to keep doses stable unless modifications are needed due to AEs, and follow the instructions regarding dose stabilization as detailed in [Appendix 9](#). Patients taking oral corticosteroids are to follow the corticosteroid taper instructions described below. Administration of prohibited UC medications, approved or investigational, constitutes treatment failure. Use of such medications should not be withheld if, in the opinion of the investigator, failure to prescribe them would compromise patient safety. Patients who require a prohibited medication to treat their UC (see [Appendix 8](#)) need to be discontinued from study drug and complete an ETV and post-treatment follow-up visits.

If a concomitant medication is needed to treat an AE or for appropriate medical management, the investigator should base decisions on the patient and clinical factors, considering prohibited medications. Local administration of corticosteroids (for example, intranasal, inhaled, intraarticular) are allowed as required for the management of pre-existing conditions and AEs. A patient who initiates a prohibited medication for a non-UC indication may either discontinue the study drug, or discontinue the prohibited medication.

Use of BCG vaccination is prohibited throughout the duration of the study and for 12 months after discontinuation of study drug. Use of nonlive (killed, inactivated or subunit) vaccinations are allowed for all patients; however, their efficacy with concomitant mirikizumab is unknown. Use of live, attenuated vaccines are prohibited during the study and for 3 months after discontinuation of study drug.

The list of prohibited medications and the list of permitted medications with dose stabilization guidance are provided in [Appendix 8](#) and [Appendix 9](#), respectively.

Corticosteroid Taper

Patients who enter Study AMBG on corticosteroid therapy for treatment of their UC and who achieved clinical response in the induction study AMAN will initiate corticosteroid tapering, as described below, at Week 0 of Study AMBG. Clinical nonresponders who undergo extended IV induction with mirikizumab will begin corticosteroid tapering if clinical response is achieved at Week 12 of the extended induction dosing, or earlier if symptomatic improvement, based on investigator discretion, is evident at any time after starting extended IV induction dosing.

For patients who cannot tolerate the corticosteroid taper without recurrence of clinical symptoms, corticosteroid taper may be paused and/or corticosteroid dose may be increased up to the original dose at induction baseline (should not exceed induction baseline dose). In such cases, attempts to reinitiate corticosteroid tapering should be made within 2 weeks of interruption of taper, with a goal to complete tapering no later than Week 12 of Study AMBG.

The recommended tapering schedule for oral corticosteroids (other than budesonide extended release tablets [budesonide MMX] or beclomethasone dipropionate [gastro-resistant prolonged-release tablet]) is as follows:

- Dose >10 mg/day prednisone or equivalent: taper daily dose by 5 mg/week until receiving 10 mg/day, and then continue tapering at 2.5 mg/week until 0 mg/day.
- Dose ≤10 mg/day prednisone or equivalent: taper daily dose by 2.5 mg/week until 0 mg/day.

The recommended tapering schedule for patients receiving oral budesonide MMX 9 mg/day is to reduce tablets to 9 mg every other day for 2 weeks, followed by 9 mg every third day for 2 weeks, and then discontinue.

The recommended tapering schedule for patients receiving oral beclomethasone dipropionate (gastro-resistant prolonged-release tablet) 5 mg/day is to reduce tablets to 5 mg every other day for 4 weeks, and then discontinue.

7.8. Treatment after the End of the Study

7.8.1. Study Extensions

Patients who complete Week 40 in Study AMBG will be assessed for eligibility to enter the open-label extension study (Study AMAP). There is no extension period within Study AMBG. If patients do not meet enrollment criteria for Study AMAP or opt not to continue into Study

AMAP, they will be asked to complete the post-treatment follow-up period, as described in the Schedule of Activities (Section 2), which will complete their study participation.

7.8.2. Treatment after Study Completion

Mirikizumab will not be made available to patients after conclusion of the study.

7.8.3. Special Treatment Considerations

7.8.3.1. Premedication for Infusions

Premedication for the study drug infusions or injections is not planned. Any premedication for infusions or injections should be discussed with the medical monitor. Any premedication given will be documented as a concomitant therapy.

7.8.3.2. Management of Hypersensitivity, Infusion-Related Events, Infusion Site Reactions and Injection Site Reactions

During and after study drug administration, patients should be closely monitored for signs or symptoms of AEs, including hypersensitivity events, other infusion-related events, and infusion or injection site reactions.

Hypersensitivity Events

If a patient experiences a systemic hypersensitivity reaction involving the skin or mucous membranes, respiratory, cardiovascular, gastrointestinal, or urinary systems, during or up to 6 hours after an infusion of study drug, the following guidance should be followed (see [Appendix 10](#) for additional information):

- Study drug infusion should be stopped immediately and appropriate supportive care provided according to local standard practice (for example, administration of epinephrine, anti-histamine, systemic steroids, and/or bronchodilators).
- After patient's stabilization, an anti-drug antibody (ADA) and PK sample should be collected; additional samples should be obtained 4 and 12-16 weeks after the event. These samples will also be used for tryptase, complement (C3/C4), and cytokine panel assays.
- The patient should be monitored until resolution or stabilization of the symptoms, as clinically appropriate.
- Study drug should be permanently discontinued after a systemic drug administration reaction. The patient should undergo post-treatment follow-up procedures after study drug discontinuation.
- The medical monitor should be notified as soon as feasible.

Other Infusion-Related Events and Infusion Site Reactions

If a patient experiences a reaction consisting of headache, rigors and/or temperature $>38^{\circ}\text{C}$ (in the absence of signs or symptoms of a systemic hypersensitivity reaction), or an infusion site reaction, including urticaria, pruritus, or angioedema localized to the IV infusion site (in the absence of other systemic hypersensitivity signs or symptoms), during or up to 6 hours after an infusion of study drug, the following guidance should be followed:

- Study drug infusion should be interrupted and appropriate medical care should be administered (for example, NSAIDs, anti-pyretics or antihistamines).
- An ADA and PK sample should be collected at the time of the event (or as soon as possible after the event occurs), and 4 and 12-16 weeks after the event. These samples will also be used for tryptase, complement (C3/C4), and cytokine panel assays.
- Resumption of study drug infusion after interruption, possibly at a slower rate of administration, can be considered if symptoms resolve and it is deemed to be medically appropriate based on the investigator's discretion, and considering the risk/benefit of readministration.
- If the patient develops systemic hypersensitivity symptoms or signs, they should be managed as described above for a systemic hypersensitivity reaction. Patient should remain in observation, as is clinically appropriate for the patient's symptoms.
- Premedication prior to subsequent study drug administration may be considered, if judged by the investigator to be appropriate for the individual patient.

Injection Site Reactions

If a patient experiences an injection site reaction, including pain, erythema, urticaria, pruritus, or angioedema localized to the SC injection site (in the absence of systemic hypersensitivity signs or symptoms), the following guidance should be followed:

- Patient should be instructed to contact the study site to report any symptoms experienced following a SC injection.
- If the patient develops systemic hypersensitivity symptoms, they should be managed as described above for a systemic hypersensitivity reaction.
- Premedication prior to subsequent study drug administration may be considered as appropriate for the individual patient.

8. Discontinuation Criteria

8.1. Discontinuation from Study Treatment

8.1.1. *Permanent Discontinuation from Study Treatment*

Study treatment may be permanently discontinued during the study. Patients who discontinue study treatment early will undergo early termination procedures, which include an ETV and post-treatment follow-up visits. The investigator will also complete any AE reporting and follow-up that may be required (if applicable, see Section 9.2).

If a patient's study treatment is discontinued before the end of the Maintenance Study Dosing Period, the patient should complete the ETV and post-treatment follow-up period as follows:

- Patients who discontinue investigational product during **extended induction IV dosing** or **before receiving any SC dosing** will return for post-treatment follow-up visits (Visit 801 and 802) 4 and 16 weeks after the end-of-treatment visit.
- Patients who discontinue study drug **after having received ≥ 1 SC dose** will return for post-treatment follow-up visits (Visit 801 and 802) 4 and 12 weeks after the end-of-treatment visit.

Possible reasons leading to permanent discontinuation of investigational product include the following (list is not exhaustive):

Patient Decision

- The patient requests to discontinue investigational product.

Discontinuation due to a hepatic event or liver test abnormality

- Patients who are discontinued from investigational product due to a hepatic event or liver test abnormality should have additional hepatic safety data collected via the hepatic eCRF packet.

Discontinuation of the investigational product for abnormal liver tests **should be** considered by the investigator when a patient meets one of the following conditions after consultation with the Lilly-designated medical monitor:

- Alanine aminotransferase (ALT) or aspartate aminotransferase (AST) $>8x$ upper limit of normal (ULN)
- ALT or AST $>5xULN$ for more than 2 weeks
- ALT or AST $>3xULN$ and total bilirubin level (TBL) $>2xULN$ or international normalized ratio >1.5
- ALT or AST $>3xULN$ with the appearance of fatigue, nausea, vomiting, right upper-quadrant pain or tenderness, fever, rash, and/or eosinophilia ($>5\%$)
- Alkaline phosphatase (ALP) $>3xULN$

- ALP >2.5xULN and TBL >2xULN
- ALP >2.5xULN with the appearance of fatigue, nausea, vomiting, right quadrant pain or tenderness, fever, rash, and/or eosinophilia (>5%)

Discontinuation due to Lack of Clinical Benefit or Disease Worsening

- Induction study responders who experience LOR and do not receive clinical benefit from mirikizumab IV rescue induction
- Induction study nonresponders who do not achieve clinical response with 3 doses of mirikizumab IV extended induction
- Induction study nonresponders who achieve clinical response with mirikizumab extended IV induction, but subsequently lose clinical benefit with open-label mirikizumab SC dosing, should be discontinued. Loss of clinical benefit may be based on demonstrating LOR criteria (see Section 5.1) or by other criteria according to investigator discretion
- Patients who require treatment with a prohibited UC medication ([Appendix 8](#)), an increase in immunomodulatory medication, or a course of corticosteroids that exceeds the baseline dose
- Patients who undergo surgery for UC

Safety Criteria for Study Drug Discontinuation

- The patient requires a prohibited medication to treat their UC ([Appendix 8](#)). A patient who initiates a prohibited medication for a non-UC indication may either discontinue the study drug, or discontinue the prohibited medication.
- The patient requires a colectomy, proctocolectomy, or partial colectomy during the study.
- A diagnosis of cancer, other than squamous cell or basal cell carcinoma of the skin, during the study.
- Dysplasia occurring in flat mucosa or DALM.
- A diagnosis of active TB during the study.
- A diagnosis of HIV/AIDS during the study.
- A diagnosis of hepatitis B during the study or development of detectable HBV DNA during the study (see Section [9.4.5.2](#)).
- A diagnosis of hepatitis C during the study or development of detectable hepatitis C virus (HCV) RNA during the study (see Section [9.4.5.4](#)).
- The patient becomes pregnant. Pregnant patients **will not** undergo an endoscopy at the ETV.
- The participant has an AE or SAE which, in the opinion of the investigator or sponsor, would preclude the participant from continuing to receive study drug.

- Systemic hypersensitivity event or anaphylaxis to study drug.

It is recommended that the patient be assessed by an appropriately trained professional to assist in deciding whether the patient is to be discontinued from the study if:

- The patient scores a 3 for Item 12 (Thoughts of Death or Suicide) on the Quick Inventory of Depressive Symptomatology—Self-Report (16 Items) (QIDS-SR16) at any time in the study, or
- The patient reports suicidal ideation or suicide-related behaviors during the study

Other Reasons for Study Drug Discontinuation

- If an investigator, site personnel performing assessments, or patient is unblinded, the patient must be discontinued from the study drug and continue to post-treatment follow-up. In cases where there are ethical reasons to have the patient continue on study drug, the investigator must obtain specific approval from the sponsor or designee for the patient to continue in the study.
- Inadvertent enrollment (see Section 8.1.3)

Patients discontinuing from the investigational product prematurely for any reason should complete AE and other follow-up procedures per Section 2 (Schedule of Activities), Section 9.2 (Adverse Events), and Section 9.4 (Safety) of this protocol.

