Notes: All activities should be completed prior to any study drug administration unless otherwise stated. Last visit or ETV is last visit prior to entering long term extension Study AMAP or post-treatment follow-up. Post-treatment follow-up visits should only occur if the patient is not proceeding to long term extension Study AMAP or if they discontinue treatment in Study AMBG early.

- a V1 (Week 0) should occur no more than 14 days from the start of the Visit 5/Week 12 visit of Study AMAN.
- b Patients who discontinue study drug with last dose administered IV will return for an LV +16 week post-treatment follow-up visit without a 12 week follow-up. Patients who discontinue study drug with last dose administered SC will return for an LV + 12 week post-treatment follow-up visit without a 16 week follow-up.
- c Results from Week 12 of Study AMAN will be used for Week 0 of this study.
- d Activity to be performed on a subpopulation of patients. See Notes column in table.
- e These tests will be run from the “chemistry” sample.

Table AMBG.2.2. Schedule of Activities – Nonresponders from Induction Study

Procedure	Extended Induction			Open-Label Maintenance Period									Post-treatment Follow-up		Notes	
	V1	V2	V3	V4 ^a	V5	V6	V7	V8	V9	V10	V11	V997	801	802		
Week	0	4	8	12	16	20	24	28	32	36	40 LV	ETV	UV	LV +4	LV +12/16 ^c	
Day and/or Visit Interval Tolerance	1 ^b	29 +/-3	57 +/-3	85 +/-7	113 +/-7	141 +/-7	169 +/-7	197 +/-7	225 +/-7	253 +/-7	281 +/-7		N/A	+/-10	+/-10	
Informed consent	X															Patients may consent between the start of V5 of Study AMAN and before any procedures at V1/Week 0 are performed.
Inclusion and exclusion criteria	X															Can begin at Week 12 of induction and continue until dosing is initiated in Study AMBG.
Concomitant medication	X	X	X	X	X	X	X	X	X	X	X	X	X	X	X	
Review AEs	X	X	X	X	X	X	X	X	X	X	X	X	X	X	X	
Tobacco/nicotine use	X ^d			X			X				X	X				
IP Administration																
IWRS/Randomization	X															
Open-label mirikizumab extended IV dosing	X	X	X													
Open-label mirikizumab SC dosing				X	X	X	X	X	X	X						
Physical Examination																
Vital signs (T, BP, and PR)	X	X	X	X	X	X	X	X	X	X	X	X	X	X	X	
Weight	X ^d			X			X				X	X				
Physical examination	X ^d										X	X				
Evaluate for EIMs	X	X	X	X	X	X	X	X	X	X	X	X	X			See Section 9.1.3.2.
12-lead ECG	X ^d										X	X				
Laboratory Investigations																

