SC dosing should be continued according to dosing schedule until endoscopy determines whether LOR is confirmed. If LOR is confirmed based on endoscopy at or after Week 12 (and *C. difficile* stool toxin testing is negative), patients will be rescued with open-label 300 mg mirikizumab Q4W IV for 3 doses. The first IV rescue dose may be administered as soon as LOR is confirmed by centrally read endoscopy, if ≥ 7 days from the most recent SC dose. Subsequent doses will be given every 4 weeks for total of 3 doses.

If endoscopy does not confirm secondary LOR, patients are encouraged to continue SC study drug dosing, maintaining the scheduled dosing interval. If study drug dosing is continued, an additional endoscopy would be performed at Week 40, early termination visit (ETV) or unscheduled visit (UV).

Patients who, in the opinion of the investigator, receive clinical benefit after completion of the LOR rescue therapy (12 weeks after first IV rescue dose) may be considered for enrollment into the long term extension study I6T-MC-AMAP (AMAP) to receive further SC dosing. Once the LOR IV rescue therapy is initiated, no further SC dosing will be available in AMBG.

If study drug is discontinued, procedures for early termination from study drug will be performed and the patient should undergo post-treatment follow-up as described in the schedule of activities (Section 2).

- **Placebo Responders from Study AMAN**

Patients who achieve clinical response with blinded placebo in the induction study will continue to receive blinded placebo for the remainder of the maintenance study. Placebo SC injections will be administered Q4W to maintain study blind. If LOR is confirmed based on endoscopy at or after Week 12 (and *C. difficile* stool toxin testing is negative), patients will be rescued with open-label mirikizumab 300 mg Q4W IV for 3 doses. The same LOR assessments and procedures should be performed as described for the mirikizumab responders from Study AMAN.

- **Mirikizumab and Placebo Nonresponders from Study AMAN**

Patients who do not achieve clinical response to blinded mirikizumab or blinded placebo in Study AMAN will receive open-label extended induction therapy with 300 mg mirikizumab IV at Weeks 0, 4, and 8, and undergo endoscopy at Week 12.

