Patients who achieve delayed clinical response (compared to induction study baseline) with extended mirikizumab induction therapy at Week 12 may subsequently receive open-label 200 mg mirikizumab Q4W SC starting at Week 12. Patients will continue on this dose regimen and undergo endoscopy at Week 40. Patients who, in the opinion of the investigator, receive clinical benefit may be considered for enrollment into the long term extension study AMAP to receive further SC dosing. Patients who discontinue study drug before Week 40 will undergo endoscopy and procedures for early termination of the study drug, including post-treatment follow-up as described in the schedule of activities (Section 2).

Patients who do not achieve clinical response to mirikizumab IV extended induction therapy at Week 12, compared to induction baseline, will discontinue study drug and undergo procedures for early termination of the study drug, including post-treatment follow-up as described in the schedule of activities (Section 2).

Post-Treatment Follow-up Period

Patients will undergo a maximum 16-week post-treatment follow-up period:

- Patients who discontinue study drug with **last dose administered IV** will return for post-treatment follow-up visits (Visit 801 and 802) at 4 and 16 weeks after the end-of-treatment visit.
- Patients who discontinue study drug with **last dose administered SC** will return for post-treatment follow-up visits (Visit 801 and 802) at 4 and 12 weeks after the end-of-treatment visit.
- Patients who subsequently enter the long term extension study AMAP do not need to complete the post-treatment follow-up period.

Figure AMBG.5.1 illustrates the study design. Study governance considerations are described in detail in Appendix 3.

[figure not shown]

Figure AMBG.5.1. Illustration of study design for Clinical Protocol I6T-MC-AMBG.

Footnotes for Figure AMBG.5.1

Abbreviations: D/C = discontinue; IV = intravenous; LOR = loss of response; Miri = mirikizumab; OL = open-label; PBO = placebo; Q4W = every 4 weeks; R = randomization; RB = rectal bleeding; SC = subcutaneous; SF = stool frequency; W = week.

Note: LOR is defined as ≥ 2 -point increase from maintenance baseline in the combined SF + RB scores, AND combined SF + RB score of ≥ 4 on 2 consecutive visits, AND confirmed by an endoscopic subscore of 2 or 3.

a = Loss of response at or after Week 12 and up to and including Week 28.

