6.3. Lifestyle Restrictions

Study participants should be instructed not to donate blood or blood products during the study and for 20 weeks following their last dose (if last dose is given IV) or for 16 weeks following their last dose (if last dose is given SC). In order to participate in the study, patients must agree to the contraception, reproduction and breastfeeding criteria detailed in inclusion criterion [4] and exclusion criterion [19].

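### Section 8.1.1 sets 12 weeks of follow-up for anyone who has had an SC dose, contradicting the 16 weeks that Sections 2 and 5.1 require after IV rescue

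*Protocol*

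**What the plan says.** The protocol gives two rules for the timing of the last post-treatment visit (Visit 802).

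- **Section 8.1.1** goes by dosing history and applies to patients who stop before the end of the maintenance dosing period. Anyone who stops "after having received ≥ 1 SC dose", it says, "will return for post-treatment follow-up visits (Visit 801 and 802) 4 and 12 weeks after the end-of-treatment visit". The 4-and-16-week schedule is reserved for those who stop during extended IV induction or before any SC dose. Neither bullet mentions IV rescue.
- **Section 5.1** (post-treatment follow-up period) goes by the route of the last dose. Patients whose last dose was IV "will return for post-treatment follow-up visits (Visit 801 and 802) at 4 and 16 weeks after the end-of-treatment visit"; those whose last dose was SC return at 4 and 12 weeks.
- **Table AMBG.2.1, footnote b**, the schedule for induction responders, agrees with Section 5.1: "Patients who discontinue study drug with last dose administered IV will return for an LV +16 week post-treatment follow-up visit". It adds that these patients have no 12-week visit.

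Section 8.1.1 also lists, among its reasons for stopping, "Induction study responders who experience LOR and do not receive clinical benefit from mirikizumab IV rescue induction". On rescue, Section 5.1 says: "Once the LOR IV rescue therapy is initiated, no further SC dosing will be available in AMBG".

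**The concern.** The two rules agree for a patient who goes from IV to SC dosing, as induction nonresponders do. They disagree for a patient who goes from SC to IV, and that is the path of every rescued induction responder. Section 8.1.1 names these patients as a discontinuation group, so the conflict is not hypothetical.

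A site that opens the discontinuation section when a rescued patient stops would book Visit 802 at 12 weeks. In Table AMBG.2.1 that visit carries adverse event review, vital signs, a pregnancy test, hematology, chemistry, and PK and anti-drug antibody samples. Under Section 9.2.1, investigators need not actively seek adverse events once a patient has left the study, so active safety surveillance would end 4 weeks early after 300 mg IV.

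The rule also sits oddly for patients on SC placebo, including those who responded to placebo in induction. Their inert injections would shorten the follow-up after active IV drug.

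**Working it through.** **1. Which patients fall under both rules.**

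- Induction responders receive SC study drug at Weeks 0, 4 and 8 (Table AMBG.7.1).
- Loss of response cannot be confirmed by endoscopy before Week 12 (Section 5.1), so rescue follows SC dosing. Appendix 2, footnote f, likewise speaks of at least 3 maintenance SC doses.
- Rescue is three IV doses 4 weeks apart, given in place of SC dosing (Table AMBG.2.1), and no SC dose follows it in this study (Section 5.1).

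Every rescued patient therefore meets the condition of the second bullet of Section 8.1.1 and also has an IV last dose. The first bullet cannot apply, because rescue is not extended induction and SC doses have been given.

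| Rule | Basis | Visit 802 for a rescued patient |
|---|---|---|
| Section 8.1.1, second bullet | any SC dose received | 12 weeks |
| Section 5.1 | route of last dose | 16 weeks |
| Table AMBG.2.1, footnote b | route of last dose | 16 weeks, no 12-week visit |

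**2. Whether the visit tolerance absorbs the difference.** Table AMBG.2.1 allows ±10 days. In days after the end-of-treatment visit:

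- Section 8.1.1: 12 × 7 = 84, so 84 ± 10 = days 74 to 94.
- Section 5.1 and footnote b: 16 × 7 = 112, so 112 ± 10 = days 102 to 122.
- Difference between targets: 112 − 84 = 28 days. Gap between windows: 102 − 94 = 8 days.

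No single visit date satisfies both rules.

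**3. Time since the last IV dose for a patient who completes rescue.** Doses are given 0, 4 and 8 weeks after rescue starts, and benefit is judged 12 weeks after the first (Section 5.1). The last dose is therefore 12 − 8 = 4 weeks before that assessment. Taking the assessment as the end-of-treatment visit:

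- Section 8.1.1: 4 + 12 = 16 weeks after the last IV dose.
- Section 5.1 and footnote b: 4 + 16 = 20 weeks.

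The blood-donation restriction in Section 6.3 applies "for 20 weeks following their last dose (if last dose is given IV) or for 16 weeks following their last dose" if that dose is SC. The 20 weeks matches the IV period; the 16 weeks matches the SC period. As a check on ordinary SC patients: last SC dose at Week 36, last visit at Week 40, so 4 + 12 = 16 weeks, which again matches Section 6.3. The rule based on the last dose fits the rest of the protocol.

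**4. When Section 8.1.1 applies.** Rescue may start from Week 12 to Week 28, and assessment is 12 weeks later.

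| Rescue starts | Benefit assessed |
|---|---|
| Week 12 | Week 24 |
| Week 20 | Week 32 |
| Week 24 | Week 36 |
| Week 28 | Week 40 |

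Rescue started at Weeks 12 to 20 is assessed at Weeks 24 to 32, before the last scheduled SC dose at Week 36. Rescue started at Weeks 24 to 28 is assessed at Weeks 36 to 40 and may fall outside Section 8.1.1. A patient who stops part-way through rescue, for example after a systemic hypersensitivity reaction (Section 7.8.3.2), stops with rescue dosing still outstanding. The 16-versus-20-week comparison in step 3 does not apply to that patient, but the 28-day difference does.

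**The case against.** The strongest reply is that the intended rule is not in doubt. In Table AMBG.2.1 the only IV dosing is rescue, so footnote b addresses exactly these patients. The rescue text in Section 5.1 sends patients who stop study drug to the Section 2 schedule for follow-up. Section 8.1.1 itself closes by saying that patients who stop "prematurely for any reason should complete AE and other follow-up procedures per Section 2 (Schedule of Activities". On this reading the two bullets were written with the nonresponders' IV-then-SC sequence in mind and overlooked rescue.

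The clinical loss also looks small. Section 5.4 gives a half-life of about 10 days:

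- 16 weeks is 112/10 = 11.2 half-lives and 20 weeks is 140/10 = 14, so well under 0.1% of the drug would remain at either point.
- Even if the end-of-treatment visit fell on the day of the last dose, 12 weeks is 84/10 = 8.4 half-lives, and 2^−8.4 is about 0.3%.

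No visit is dropped, only moved earlier, and related serious events learned of after discharge must still be reported (Section 9.2.1). Section 6.3 is a blood-donation rule, not a follow-up requirement. The maintenance dosing period is not defined in Section 8.1.1, so whether a patient who has completed all three rescue doses stops before its end can be argued.

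All of this stands as a limit on the importance of the point. It does not remove the contradiction: the cross-references show what was meant, but the explicit 12-week instruction remains in the section a site consults at discontinuation, and the protocol states no order of precedence.

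**Conclusion.** The concern holds. The second follow-up bullet of Section 8.1.1 is wrong as written for induction responders, on mirikizumab or placebo, whose last dose is IV rescue and who stop early without entering the extension study. It puts Visit 802 at 12 weeks where Section 5.1 and Table AMBG.2.1 require 16. The difference is 28 days per affected patient, and the windows do not overlap.

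The consequence is confined to 4 weeks of adverse event and laboratory follow-up and an earlier final PK and antibody sample. Little residual drug is expected by either date, on the protocol's approximate 10-day half-life. The number of patients affected cannot be derived, because the protocol gives no expected rate of loss of response or of stopping after rescue. Induction nonresponders are unaffected, as are the primary endpoint, power and type I error. This is a drafting contradiction in a safety instruction; the design itself is not in question. It should be corrected.

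**What to change.** Replace both follow-up bullets in Section 8.1.1 with the rule already used in Section 5.1 and Section 2:

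- last dose IV, whether extended induction or rescue: Visits 801 and 802 at 4 and 16 weeks after the end-of-treatment visit;
- last dose SC: Visits 801 and 802 at 4 and 12 weeks after it.

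Naming rescue in the first bullet closes the gap. Patients whose last dose is SC stay at 12 weeks, and those who stop during extended induction stay at 16. The cost is two reworded bullets in the next amendment or a clarification letter to sites, with no visit or procedure beyond those in Table AMBG.2.1.
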